Official Title: A PATH (Promoting Activity and Trajectories of Health) for Children

NCT Number: NCT03189862

Document Date: 8/17/2017

Statistical Analysis Plan

Analyses of primary outcomes

Before conducting outcome analysis, we will examine the range and frequency distributions for all variables and will transform variables when appropriate. Preliminary analyses will assess each outcome cross-sectionally at baseline and at all follow-up time points. We will compare study groups (ie, CHAMP vs Control) for comparability and change in variables over time. To study both the short-term (immediate) and long-term (sustainable) effects of CHAMP, we will assess all longitudinal outcomes by both summary statistics and descriptive data figures over the baseline, post-intervention and the start and end of the academic year during Years 2, 3 and 4. Since the samples will be collected in different classrooms and different preschools, our data will have a clustered structure, which means within-cluster correlations likely exist.

For such clustered longitudinal data, we will use primarily random effects in the following models to account for multilevel correlations among the measurements: Mixed Model Regression, Growth Curve Modelling and Structural Equation Modelling.⁹³⁻⁹⁶ Random effects are appealing here to account for some latent mediating factors that may exist in the study. We will use the Mixed Model Regression to determine the effects of our proposed intervention on primary and secondary outcomes (Aim 1 and 2). Growth Curve Models will be used to understand if, and how, time-course changes in motor performance, perceived physical competence and physical activity differ between the intervention and control groups and Structural Equation Modelling for mediation analysis (Aim 3).

More specifically, in Aim 1, the immediate post-intervention effect of CHAMP (compared with control participants) on each outcome variable will be evaluated at post-intervention (Month 9). We will examine descriptive statistics on both pre-intervention and post-intervention measures of the outcome variables for each group. The change in motor performance, perceived physical competence and physical activity (ie, physical activity refers to time spent in MVPA) will be compared between two groups using regression models, adjusting for other confounding factors (eg, age and sex). Random effects will be included in the model to accommodate the potential within-cluster correlation coming from the nature of how the data are collected. We will investigate the amount of attrition from pre-intervention to post-intervention, and attempt to identify the baseline predictors of the likelihood of dropping out (as an indication of possible bias in the change estimates).

In Aim 2, we will use Mixed Model Regression to analyse the clustered longitudinal data from our RCT to assess the long-term effects of the CHAMP intervention on improving the three outcome measures: motor performance, perceived physical competence and physical activity. In this analysis, we can obtain the estimates of the long-term longitudinal intervention effect by adjusting for confounding factors that include sex and age. For physical activity and BMI, we will test for a possible delay before any significant change because of the difficulty of achieving health behaviour change by adding time-lagged covariates related to behaviour changes in the regression analysis. We will also conduct exploratory analyses to test interaction effects to understand potential modified intervention effects by different levels of behaviour changes. The intervention is designed to promote a positive trajectory of children's motor performance, perceived physical competence, and physical activity, and we will specifically test interactions between intervention and time and between baseline motor skills, perceived physical competence, and time to see which baseline measure is a stronger driver of increasing physical activity.

In Aim 3, we will apply the Growth Curve Models to understand if, and how, time-course changes in motor performance, perceived physical competence and physical activity differ between the intervention and control groups. This model is also used to determine a time

window over which the intervention effect appears stronger. We will use Structural Equation Models to determine which hypothesised constructs might be responsible for the intervention effect on longitudinal physical activity. Based on the results of our previous work, for example, we hypothesise that perceived physical competence will not mediate the relationship between motor performance and physical activity at baseline, but perceived physical competence will mediate the relationship between motor performance and physical activity immediately post-intervention and across the 3-year follow-up period. We will use Mplus software to fit Structural Equation Models, and the goodness of fit of Structural Equation Models will be assessed using multiple criteria such as χ^2 to df ratio (<2) and the root mean square error of approximation (<0.05).

Our goal is to have limited missing data but there is a potential for missing data. Assuming that data are missing at random, multiple imputation techniques will be used to replace missing data.⁹⁷ Missing data will be assumed to be missing at random if no participant demographics or primary outcomes are correlated with missingness. Mixed-effects models allow for partial information to be included for individuals who may dropout before any post-intervention data collection periods. Missing values will be multiply imputed using available covariates by sequential imputation. This approach allows optimal use of the available data in analysis involving change measures.

Data management

Extreme care to ensure high-quality and secure data will be exercised. All data will be stored securely at the University of Michigan and partial data (product measures) at the University of South Carolina. All data will have only a numerical identifier so that individual respondents, except for video data, cannot be identified. All data will be reported as aggregate statistics and no individuals will be recognisable from the data reported. All data will be perused for consistency, errors of omission and appropriateness of the response. Once a coded and cleaned data file has been prepared, frequency distributions and descriptive statistics (means, SD and ranges) for each of the measured variables will be used for consistency checks and to verify the comparability of the groups. Logic check programmes will be run to ensure that each data point falls within the expected range or corresponds to possible values in the codebook. These tracking system files will be maintained on a secure server at the University of Michigan. Data will be analysed using SAS 9.3.^{97 98} All members of the study team will be required to complete the web-based National Institutes of Health University of Michigan Responsible Conduct of Research training programme. The investigative team will engage in the ongoing data management training, data monitoring and measurement training throughout the investigation.

Statistical Analysis Plans, Power considerations, and Data management for Self-regulation measures (Supplemental Award)

Overall Analysis Plans. We will apply transformations to assure normality, run descriptive statistics, and assess potential covariates to include. While maximum effort will be made to retain all participants and minimize the amount of missing data, we anticipate there will be some data lost-to-follow-up and incomplete measures. Therefore, we will address missing data in the analysis plan by applying advanced statistical techniques, such as “multiple imputations” using PROC MI in SAS and IVEWARE SAS macro. Our overall approach will be to employ multivariate analysis to assess associations among key variables using the appropriate models based on the distribution of the data (i.e., normal, categorical data, count data, reaction time data). Since this is a cluster-randomized trial, adjusting the covariates (e.g., child sex, age, race/ethnicity) will aid in controlling additional unbalancesess due to the limited sample size. All analysis will be done using SAS 9.3 or R 4.1.0⁹⁶⁻⁹⁸. Additionally, we will perform “intent to treat”

analysis and assume all subjects comply to the assigned group. Findings/results from the study will also follow the CONSORT guidelines.

Power considerations. When we calculate the sample size and power, we assumed the intra-cluster correlation is 0.3. The achievable power is calculated for a detectable effect size, which is the detectable mean difference standardized by the square root of sample variance. Given the randomization design with 70 children in the intervention group and 50 children in the control group, we have 80% power to detect a difference in cognitive SR, behavioral SR, or emotional SR with an effect size of 0.52 and a Type I error level of 0.05.

Specific analysis plan for Aim 1. Examine the immediate (pre- to post-test) intervention effects of CHAMP (compared to control participants) on cognitive SR (cognitive flexibility, working memory, attention shifting), behavioral SR (behavioral inhibition), and emotional SR (emotion regulation). The immediate post-intervention effect of CHAMP (compared to control participants) on each SR outcome variable will be evaluated at post-intervention. We will examine descriptive statistics for both pre-and post-intervention SR outcome variables for each group. The change in cognitive SR, behavioral SR, and emotional SR scores will be compared between the intervention (CHAMP) and control groups using regression models, adjusting for other confounding factors. We assume randomization will be successful and we will monitor throughout the trial. It is always good practice to monitor along the way and we will do so, but randomization may be imperfect as this is a randomized cluster trial taking place in the real world (i.e., Head Start setting). If randomization does not work this will lead to biased results and methodology, our planned analyses to adjust other variables will be considered. Random effects will be included in the model to accommodate for the potential within-cluster correlations due to nested classroom data. We anticipate that some children will have only partial adherence to the intervention (i.e., attend a subset of sessions), thus we will also conduct a dose-response analysis where dose corresponds to number of sessions. We will investigate the amount of attrition from pre-to post-intervention, and attempt to identify baseline (or pre-intervention) predictors of dropping out. The information will indicate possible bias in the change estimates.

Specific analysis plan for Aim 2. Examine the associations between SR (cognitive SR, behavioral SR, and emotional SR) and changes in health behaviors (motor competence, perceived competence, physical activity) and health outcomes (body mass index, waist circumference). We will further evaluate the associations between changes in SR and changes in children's health behaviors and outcomes, using regression models. More specifically, we will examine the strength of association between each SR variable and our outcomes of interest using bivariate analyses to compare change in SR to change in motor competence, perceived competence, and PA (using an alpha value of $p < .05$). To test whether the strength of association varies by intervention status, we will use multivariate regression models (controlling for covariates as needed) to examine the association of SR and outcomes in each group (CHAMP and control). Similarly, random effects will be included in the model to accommodate for the potential within-cluster correlations from nested classroom data. We will further apply Structural Equation Models (SEM) to evaluate whether the CHAMP intervention has a causal effect on children's health outcomes mediated through SR.

Data Management. Extreme care to ensure high-quality and secure data will be exercised. All data will be stored securely at the University of Michigan. All data will have only a numerical identifier so that individual respondents, except for video data, cannot be identified. All data will be reported as aggregate statistics and no individuals will be recognizable from the data reported. All data will be scanned for consistency, errors of omission, and appropriateness of the response, and 30% of data will be checked by a blinded member of the research team. Once a coded and cleaned data file has been prepared, frequency distributions and descriptive

statistics (means, standard deviations, and ranges) for each of the measured variables will be used for consistency checks and to verify the comparability of the groups. Logic check programs will be run to ensure that each data point falls within the expected range or corresponds to possible values in the codebook. These tracking system files will be maintained on a secure server at the University of Michigan. Data will be analyzed using SAS 9.3 or R 4.1.0 ⁹⁶⁻⁹⁹. All members of the study team will be required to complete the web-based National Institutes of Health University of Michigan Responsible Conduct of Research Training Program. The investigative team will engage in ongoing data management training, data monitoring, and measurement training over the course of the investigation. Rewards and incentives will be incorporated after each assessment time point to aid in participant engagement.

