Aim 1: Examine the immediate post-intervention effect of CHAMP (compared to control participants) on MC, PMC, and PA in preschool-age children.

The immediate post-intervention effect of CHAMP (compared to control participants) on each outcome variable will be evaluated at post-intervention (month 9). We will examine descriptive statistics on both pre- and post-intervention measures of the outcome variables for each group. The change of MC, PMC, and PA (i.e., PA refers to time spent in MVPA) will be compared between two groups using regression models, adjusting for other confounding factors. Random effects will be included in the model to accommodate for the potential within-cluster correlation coming from the nature of how the data are collected. We will also investigate the amount of attrition from pre-intervention to post-intervention, and attempt to identify baseline (or pre-intervention) predictors of the likelihood of dropping out (as an indication of possible bias in the change estimates).

Aim 2: Assess the sustainable effect of CHAMP (compared to control) on MC, PMC, and PA across middle childhood.

We will use MMR to analyze the clustered longitudinal data from our RCT to assess the long-term effects of the CHAMP intervention on improving the three (3) outcome measures, MC, PMC, and PA. In this analysis, we can obtain the estimates of the long-term longitudinal intervention effect, by adjusting for confounding factors (i.e., sex). For PA, we will test for a possible delay before any significant change because of the difficulty of achieving health behavior change by adding time-lagged covariates related to behavior changes in the regression analysis. We will also conduct exploratory analyses to test interaction effects to understand potential modified intervention effects by different levels of behavior changes. The intervention is designed to promote a positive trajectory of children's MC, PMC, and PA, and we will specifically test interactions between intervention and time, and between baseline motor skill and time, to see which baseline measure is a stronger driver of increasing physical activity.

Aim 3: Examine and compare the immediate and long-term mediating effect of PMC on the relationship between MC and PA in preschool-age children in the CHAMP and control.

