Growth Curve Models (GCM) will enable us to understand if, and how, time-course changes in MC, PMC, and PA differ between the intervention and control groups. This model is also used to determine a time window over which the intervention effect appears stronger. We will use Structural Equation Models (SEMs) to determine which hypothesized constructs may be responsible for intervention effect on longitudinal PA. Based on the results of our previous work, for example, we hypothesize that PMC will not mediate the relationship between MC and PA at baseline, but PMC will mediate the relationship between MC and PA immediately post intervention and across the 3-yr follow-up period. We will use Mplus software to fit SEMs, and the goodness of fit of SEM models will be assessed using multiple criteria such as Chi-square to degrees of freedom (df) ratio (<2) and the Root Mean Squared Error of Approximation (RMSEA <0.05).

Sample Size, Power Analysis and Sample Attrition. Sample size was calculated based on our primary endpoint, the change in PA between baseline and immediate follow-up. According to previous literature³², we anticipate a change score of 12.1 minutes of MVPA/day for the intervention group after 1 year, with a conservative estimate of the standard deviation (SD) as 27 MVPA/day. Such a change is accepted as a clinically meaningful change in improving PA among preschool children. To detect an adjusted 12.1 (SD=27) difference in PA after 1 year between intervention and control groups with 90% power at an alpha level of 0.05, we will need a total of 212 subjects (106 subjects per arm). To account for a total of a 30% loss to follow-up, we will recruit 298 subjects at baseline (149 subjects per arm). To maintain the statistical power as 90%, the needed sample size and the detectable differences in change of PA scores are summarized in Figure 6.⁶⁹ Cohort feasibility data supports no difficulties identifying subjects who meet initial inclusion criteria for this study (See Approach Section C.4.4.). With the proposed sample size, the relationship between the power we can achieve for analyzing the mean change of MC score and PMC score and their corresponding expected mean difference and SD appears in Figure 7.⁶⁹ Given expected larger effects on MC and PMC, power to detect differences across groups is larger for MC and PMC than that seen with PA.

[figure not shown]

Fig 6: Sample size to achieve 90% power for PA.

[figure not shown]

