The immediate post-intervention effect of CHAMP (compared to control participants) on each SR outcome variable will be evaluated at post-intervention (month 9). We will examine descriptive statistics for both pre- and post-intervention SR measures of the outcome variables for each group. The change in *cognitive flexibility, working memory, behavioral inhibition, and emotion regulation* scores will be compared between the intervention (CHAMP) and control groups using regression models, adjusting for other confounding factors. Random effects will be included in the model to accommodate for the potential within-cluster correlations due to nested classroom data. We anticipate that some children will have only partial adherence to the intervention (i.e. attend a subset of sessions), thus we will also conduct a dose-response analysis where dose corresponds to number of sessions. We will also investigate the amount of attrition from pre- to post-intervention, and attempt to identify baseline (or pre-intervention) predictors of the likelihood of dropping out (as an indication of possible bias in the change estimates).

Aim 2. Test the hypothesis that improvement in child SR indicators (*cognitive flexibility, working memory, behavioral inhibition, and emotion regulation*) is associated with improved motor competence, perceived motor competence, and objectively-measured PA from pre- to post-test.

We will examine strength of association between each SR variable and our outcomes of interest using bivariate analyses to compare change in SR to change in motor competence, perceived motor competence, and PA (using an alpha value of $p < .05$). We will also use multivariate regression models (controlling for covariates as needed) to examine the association of SR and outcomes in each group (CHAMP and control) in order to test whether the strength of association varies by intervention status.

Sample Size, Power Analysis and Sample Attrition. The sample size was calculated based on our findings from preliminary data. After 9 months, we will be able to detect effects between intervention and control groups with 85% power at an alpha level of 0.05, with a total of 98 subjects (49 subjects per arm). To account for a total of a 16.5% loss at post-intervention, we will recruit 120 subjects (60 subjects per arm) at baseline.

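### Aim 1 compares change from baseline between arms without saying whether the outcome's own baseline is a covariate; naming it fixes the estimator in advance and usually gains precision

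*SAP*

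**What the plan says.** Four statements define the Aim 1 analysis, and all compare change between arms by regression with random effects for clustering.

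- SAP, Analyses of primary outcomes, Aim 1: the changes "will be compared between two groups using regression models, adjusting for other confounding factors (eg, age and sex").
- Protocol section E, Objective 1, Aim 1: "The change of MC, PMC, and PA (i.e., PA refers to time spent in MVPA) will be compared between two groups using regression models", with adjustment for confounders that are not listed.
- SAP, Supplemental Award, specific plan for Aim 1: "The change in cognitive SR, behavioral SR, and emotional SR scores will be compared between the intervention (CHAMP) and control groups using regression models", again adjusted for unlisted confounders. If randomisation does not work, "our planned analyses to adjust other variables will be considered". The overall plan for these measures gives sex, age and race/ethnicity as examples.
- Protocol, Objective 2, Aim 1: the SR "scores will be compared between the intervention (CHAMP) and control groups using regression models, adjusting for other confounding factors".

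In the main analyses, baseline motor skill and perceived competence enter only in the Aim 2 interactions with time.

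The protocol's sample-size section for Objective 1 states: "Sample size was calculated based on our primary endpoint, the change in PA between baseline and immediate follow-up". The target there is: "To detect an adjusted 12.1 (SD=27) difference in PA after 1 year between intervention and control groups with 90% power". It does not say what the difference is adjusted for. The only ICC in either document is for SR, where the SAP says "we assumed the intra-cluster correlation is 0.3".

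**The concern.** A plain change score subtracts the whole baseline value, whatever the correlation between baseline and follow-up. A model with baseline as a covariate estimates how much to subtract, and without clustering is more precise whenever that correlation is below 1 (equal variances). The two models generally give different estimates when the arms differ at baseline, as they will by chance with 15 classes per arm, or 10 per arm for SR.

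The plan permits both. The SAP's reference to mixed model regression does not settle the matter: baseline could be a covariate, an outcome with arm-specific means (with complete data, the change contrast) or an outcome with one common mean (a baseline-adjusted contrast). So the estimator for the primary endpoint, change in minutes of moderate-to-vigorous physical activity (MVPA), could be chosen after the data are seen, and some power may be given up for nothing.

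**Working it through.** **Step 1. Reproduce the plan's figure.** Inputs from the protocol's sample-size section: difference 12.1, SD 27, alpha 0.05 (taken as two-sided), power 90%.

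n per arm = 2(1.960 + 1.282)² / (12.1/27)² = 104.6, so 105. The t-based version gives 105.6, so the plan's 106.

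Power at 106 per arm: SE = 27√(2/106) = 3.71; 12.1/3.71 − 1.96 = 1.30; power 0.904. The stated size is therefore an unclustered comparison in which 27 is the SD of whatever is compared.

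**Step 2. Add the baseline, same unclustered inputs.** Read 27 as the SD of change. Assumptions not in the documents: equal variance σ² at both times, and pre-post correlation ρ.

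Var(change) = 2σ²(1 − ρ). Var(adjusted) = σ²(1 − ρ²). Ratio = (1 + ρ)/2. Power = Φ(3.263/√ratio − 1.96).

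| ρ | Variance ratio | SE (min) | Power |
|---|---|---|---|
| change score | 1 | 3.71 | 90% |
| 0.3 | 0.65 | 2.99 | 98% |
| 0.5 | 0.75 | 3.21 | 96% |
| 0.7 | 0.85 | 3.42 | 94% |
| 0.8 | 0.90 | 3.52 | 93% |
| 0.9 | 0.95 | 3.61 | 92% |

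**Step 3. Add clustering.** Let m be children per class, ρ the child-level and π the class-level pre-post correlation. Take total variance 1 at each time. Then:

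- variance of a class mean: A = ICC + (1 − ICC)/m
- slope between class means: B = [ICC·π + (1 − ICC)ρ/m] / A
- change score: proportional to 2A(1 − B)
- child's baseline only, fitted slope b: A(1 − 2bB + b²)
- child's baseline plus class mean: A(1 − B²)

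The ratios to the change score are (1 − 2bB + b²)/[2(1 − B)] and (1 + B)/2.

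Example: ICC 0.3, m = 6, ρ = 0.5, π = 0.95. A = 0.3 + 0.7/6 = 0.417; B = (0.285 + 0.058)/0.417 = 0.824; b = 0.593 from the random-intercept fit. Child only: (1 − 0.977 + 0.352)/0.352 = 1.06. With class mean: 1.824/2 = 0.91.

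Class sizes: 300 children in 30 classes is 10 per class, or 7 after 30% loss; 120 SR children in 20 classes is 6. Apart from the SAP's 0.3 for SR, the ICCs are assumed.

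| ICC, m | π / ρ | Child only | With class mean |
|---|---|---|---|
| 0.10, 7 | 0.5 / 0.5 | 0.75 | 0.75 |
| 0.10, 7 | 0.9 / 0.5 | 0.87 | 0.84 |
| 0.10, 7 | 0.95 / 0.3 | 0.86 | 0.79 |
| 0.20, 7 | 0.9 / 0.5 | 0.96 | 0.88 |
| 0.20, 7 | 0.95 / 0.3 | 1.05 | 0.86 |
| 0.30, 6 | 0.5 / 0.5 | 0.75 | 0.75 |
| 0.30, 6 | 0.9 / 0.5 | 1.00 | 0.89 |
| 0.30, 6 | 0.95 / 0.5 | 1.06 | 0.91 |
| 0.30, 10 | 0.9 / 0.5 | 1.12 | 0.91 |

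**Step 4. Check with few classes.** The large-sample formulas ignore the cost of estimating the extra slope. Simulation with REML random-intercept fits (6000 trials per case) shows it.

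- 30 classes of 7, ICC 0.10, equal correlations 0.3 to 0.9: child only 0.64 to 0.96; with class mean 0.66 to 0.99, about 3–4% more variance.
- SR, ICC 0.3, 10 classes of 7 and 10 of 5 (the SAP's 70/50 split spread over the protocol's 10 + 10 classes, which is an assumption), equal correlations 0.3 to 0.9: child only 0.63 to 0.95; with class mean 0.67 to 1.01, about 5–6% more.
- Same SR design, unequal correlations: at π/ρ 0.8/0.5, 0.91 and 0.90; at 0.9/0.5, 1.02 and 0.93; at 0.95/0.3, 1.16 and 0.94.

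**The case against.** The covariate lists are open, and confounder adjustment in the SR plan is stated unconditionally before the sentence about failed randomisation. An analyst could add the baseline and stay within the plan. That stands: nothing excludes it. But an open list also leaves the choice until after the data are seen.

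The power gain depends on what 27 means, and the protocol does not say. If it is the SD at one time point, the SD of change is 27√[2(1 − ρ)], and change-score power at 106 per arm is 79%, 90% and 99% at ρ 0.3, 0.5 and 0.7, so at 0.7 or above baseline adjustment adds almost nothing. If 27 already reflects baseline adjustment, there is no gain over 90%, but an unadjusted change score delivers only 75%, 81%, 85%, 87% and 89% at ρ 0.3, 0.5, 0.7, 0.8 and 0.9. The word adjusted may also mean only age and sex. This objection stands, and is a reason to state the meaning of both figures.

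A reader might infer three stronger things. One is that the change-score analysis is biased; with classes randomised it is not. Another is that SR needs the class-mean baseline; it helps clearly only when class-level correlation is well above child-level, the documents give neither, and it costs a little when they are equal. The third is that SR is a special case. It differs only in having a stated ICC; the same argument covers MVPA, motor competence and perceived competence if their ICC is similar.

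**Conclusion.** The point holds as one of precision and pre-specification. No Aim 1 statement names the outcome's own baseline, and the primary estimator is therefore not fixed. With 27 as the SD of change and no clustering, naming it lowers the variance by 35% to 5% for ρ from 0.3 to 0.9. With clustering, every case examined at ICC 0.10 or below still gains. At ICC 0.2 to 0.3, the child's baseline alone can lose to the change score, chiefly when class-level correlation is about 0.9 or more and child-level 0.5 or less; adding the class mean removes the loss, at 3–6% more variance when the two correlations are equal.

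The correlations, the equal variances and every ICC except the SAP's 0.3 for SR are assumptions. No precision claim is made for the ordinal card-sort (DCCS) score. Whether the sample size should have allowed for clustering is a separate question. The change is worth making before analysis; confidence in the size of the gain is medium.

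**What to change.** State in both documents that each Aim 1 model (MVPA, motor competence, perceived motor competence and each SR score) includes the child's baseline value of that outcome, together with the class random effect and the listed covariates. The outcome may still be called change: in a linear model, regressing change on arm plus baseline gives the same treatment effect as regressing the follow-up value. The DCCS score takes the model suited to its distribution, with its baseline as covariate.

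As a safeguard for any outcome whose ICC may be near 0.3, also pre-specify the class-mean baseline. Alternatively, specify a longitudinal mixed model with baseline means constrained equal across arms and free class- and child-level covariances between the two times.

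In the protocol's sample-size section for Objective 1, say what the 12.1 is adjusted for and whether 27 is the SD of change.

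Cost: wording, one or two degrees of freedom per model, and the small variance cost of the class mean if it turns out not to be needed. No new data are required, since the baselines are already collected at month 0.
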